The initial protocol submitted and approved by the Duke IRB was intended to focus solely on the design and procedures for Aim 1 in order to address the three aims listed below in sequential order such that the findings from Aim 1 would be used to further develop the protocol design and procedures for Aim 2, and similarly the findings from Aims 1 and 2 will strengthen the approach to Aim 3.

This study will enroll up to 40-60 total participants for Aim-2 and Aim-3. While we anticipate that the screening blood draw will yield a number of screen failures, we expect that approximately 20-25 subjects will complete Aim-2 and 15-20 will complete Aim-3 of the study protocol.

Enrolled participants for Aim-2 will be asked to complete three study visits including the consent visit and two infusion study visits that will include hyperglycemic clamps and an infusion of Exedin-9. Each

infusion procedure will last 2 hours.

AIM-2: The primary outcome for visits 2-3 will be to measure the effects of Ex-9 on fasting glucose-stimulated insulin secretion before and after experimentally induced insulin resistance. The primary experimental variable for analysis will be C-peptide during the clamp. Mean values will be compared between the period of glucose only stimulation and glucose with Ex-9. For each subject in the active treatment arm data will be analyzed using 2-way ANOVA for repeated measures using time (0-60 vs 60-120 min) and treatment (Dex vs no Dex) as the two factors. Based on our previous studies we expect a significant time effect due to Ex-9. If there is an interaction with treatment we would conclude that experimental insulin resistance influences the fasting GLP-1 effect. Data from control subjects will be analyzed identically; here we expect no interaction, indicating that the fasting GLP-1 is a stable measure. In our previous study using Ex-9 during a glucose clamp, the average coefficient of variation in insulin concentrations at the conclusion of each step in the ramp was 30%. Using this estimate of between subject variation, detecting a 20% difference between subsequent steps in the GLP-1 ramp with a power of 80% and significance level of 0.05 will require 8 subjects.

Enrolled participants for Aim-3 will be asked to complete two study visits including the consent visit and one infusion study visit that will include a hyperglycemic clamp and an infusion of Exedin-9. The infusion procedure will last 2 hours.

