AIM-3 – The primary outcome measure for this study will be the fasting GLP-1 effect. This will be defined as the difference in steady state glucose-stimulated insulin secretion with and without Ex-9. The difference will be expressed as a percentage of glucose stimulated insulin secretion without Ex-9, and serve as the primary variable for comparison among the lean, obese and diabetes cohorts.

Research Summary

State your primary study objectives

AIM-2: Determine the role of basal GLP-1 action on the β -cell response to insulin resistance. Healthy subjects will have fasting GLP-1 action determined with GLP-1r blockade before and after induction of experimental insulin resistance. We hypothesize that fasting GLP-1 action will increase to compensate for experimental insulin resistance.

AIM-3: The primary outcome measure for this study will be the fasting GLP-1 effect. This will be defined as the difference in steady state glucose-stimulated insulin secretion with and without Ex-9.

State your secondary study objectives

Please select your research summary form:

Standard Research Summary Template

This is the regular (generic) research summary template which is required for all regular applications (unless your protocol fits under the other research summary templates in this category). Use of these instructions is helpful for ensuring that the research summary contains all necessary elements.

Standard Research Summary

Purpose of the Study

Objectives & hypotheses to be tested

This protocol is funded by the Veteran's Administration and being led by [name] [name] in the Division of Endocrinology and the Duke Molecular Physiology Institute. The study will address the following three specific aims:

- 1. Determine the roles of fasting GLP-1 concentrations and alpha-cell secretion on insulin release. The first part of this aim will determine the threshold plasma concentration of GLP-1 that increases insulin secretion to test the hypothesis that fasting levels of circulating GLP-1 are insufficient to mediate β -cell secretion. The second part of the aim will determine whether the insulin response to specific amino acids is dependent on the α -cell release of GLP-1.

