- 2. **Determine the role of basal GLP-1 action on the β-cell response to insulin resistance.** Heal thy subjects will have fasting GLP-1 action determined with GLP-1r blockade before and after induction of experimental insulin resistance. We hypothesize that fasting GLP-1 action will increase to compensate for experimental insulin resistance.
- 3. Determine the role of basal GLP-1 action on fasting glucose regulation in lean, obese, pre-diabetic and diabetic subjects. A cross sectional study of age-matched subjects across the spectrum of glucose tolerance will be used to test the hypothesis that fasting GLP-1 action increases as β-cell function declines. Groups of lean, obese, pre-diabetic and type 2 diabetic (T2DM) subjects will receive exedin-9 during a graded glucose infusion. We hypothesize that the relative effect of GLP-1r blockade on insulin secretion will be greater with progression from normal to T2DM.

Initially, this study was to address these three aims in sequential order such that the findings from Aim 1 would be used to further develop the protocol design and procedures for Aim 2, and similarly the findings from Aims 1 and 2 will strengthen the approach to Aim 3. To that end, [name] has been able to address Aim 1 by collecting and analyzing data from another study with a similar protocol design. This IRB amendment is being filed to address the procedures for both Aim 2 and Aim 3.

Background & Significance

• Should support the scientific aims of the research

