Visits 2 and 3: Each participant will have two 4-hour hyperglycemic clamp procedures with the addition of the GLP-1 receptor antagonist Exendin-9 (Ex-9) to determine the *fasting GLP-1 effect*. During both visits, the participants will receive an infusion of Ex-9 beginning at the 60-minute mark of the clamp procedure; this will allow a comparison of glucose-stimulated insulin secretion with and without GLP-1 action, a parameter we have termed the *fasting GLP-1 effect*. Throughout the glucose infusions during visits 2 and 3, 1 ml blood samples will be taken every 5-10 minutes beginning at the -15 minute time-point and continue until the end of the 120 minute procedure. These samples will be tested immediately with a YSI glucose analyzer and the values used to adjust the glucose infusion rate to maintain stable blood glucose concentrations (a glucose clamp) throughout the experiment.

Subjects will report to the Duke Center for Living after a 12-hour fast. Study staff will obtain the participant's current body weight. At Visit-2 a skin test to confirm they do not have any sensitivity to the Ex-9 investigational compound that will be used during both visits 2 and 3 will be administered. The skin test is specified by the FDA as a precaution for immediate hypersensitivity; 5 ng of Ex-9 is injected intradermally and subjects are monitored for 30 minutes for a wheal/flare reaction. This skin test must be negative in order to continue with the study testing. Once a negative skin test has been recorded, the participant will not need to be retested for sensitivity to Ex-9 at visit 3.

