Subjects will have two intravenous catheters placed, one in each arm: 1) for blood drawing, and 2) for the infusion of test materials. The arm for blood draws will be heated to maintain blood flow and arterialize venous blood. Four (4.0 ml) fasting blood samples will be taken at -15, -10, -5 and 0 minutes and then a variable infusion of 20% dextrose will begin to clamp the blood glucose at basal +3 mM for 120 minutes. This hyperglycemic clamp will be stabilized over 60 minutes and 4.0 ml blood samples will be taken every 5-10 minutes during this period to establish baseline insulin secretion and active GLP-1 levels. During these visits, participants will receive an infusion of Exendin-9 (750 pmol/kg/min) between the 60 and 120 minute time-points of the clamp procedure. For consistency, blood draws (4.0 ml) will occur every 5-10 minutes between the 60 and 120 minute time-points of both visit 2 and 3. Upon completion of the final 60-minute interval for the Ex-9 infusion, both the infusion and clamp procedures will be complete. One additional blood sample (1 ml) will be drawn post the assessment to be tested immediately with the YSI glucose analyzer to ensure glucose levels are within normal limits. **Visit 3** will occur at least one week later and will be a repeat infusion procedure identical to **Visit 2**. The total amount of blood collected during each of these visits will be a maximum of ~141 ml (~9.5 Tbsp).

We will aim to complete studies in 10-15 subjects before and after approximately one week of dexamethasone(Dex) treatment to induce insulin resistance. Insulin resistance in response to a short-course (4 mg daily) of supraphysiologic glucocorticoids is an established research procedure and is completely reversible over the course of exposure we are proposing. However, the rate of reversal is variable among subjects preventing a straight counter-balanced allocation to treatment (i.e. half of subjects getting Dex before the first study and half before the second). Therefore we will enroll 6-10 subjects as controls for effects of time and repeat testing. These individuals will have identical clamps with no dexamethasone at approximately 1 week intervals and will be determined at random by study staff.

AIM-3

Approximately 15-20 subjects will complete AIM-3 of the study and these participants will have two study visits – a baseline consent visit, and one infusion procedures.

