to target accrual and accrual rate. Describe interim analysis including plans to stop accrual during
monitoring. Phase I studies, include dose escalation schema and criteria for dose escalation with
definition of MTD and DLT.

AIM-2 – The primary outcome for visits 2-3 will be to measure the effects of Ex-9 on fasting glucose-stimulated insulin secretion before and after experimentally induced insulin resistance. The primary experimental variable for analysis will be C-peptide during the clamp. Mean values will be compared between the period of glucose only stimulation and glucose with Ex-9. For each subject in the active treatment arm data will be analyzed using 2-way ANOVA for repeated measures using time (0-60 vs 60-120 min) and treatment (Dex vs no Dex) as the two factors. Based on our previous studies we expect a significant time effect due to Ex-9. If there is an interaction with treatment we would conclude that experimental insulin resistance influences the *fasting GLP-1 effect*. Data from control subjects will be analyzed identically; here we expect no interaction, indicating that the fasting GLP-1 is a stable measure. In our previous study using Ex-9 during a glucose clamp, the average coefficient of variation in insulin concentrations at the conclusion of each step in the ramp was 30%. Using this estimate of between subject variation, detecting a 20% difference between subsequent steps in the GLP-1 ramp with a power of 80% and significance level of 0.05 will require 8 subjects.

AIM-3 – The primary outcome measure for this study will be the fasting GLP-1 effect. This will be defined as the difference in steady state glucose-stimulated insulin secretion with and without Ex-9. The difference will be expressed as a percentage of glucose stimulated insulin secretion without Ex-9, and serve as the primary variable for comparison among the lean, obese and diabetes cohorts.

Data & Safety Monitoring

Summarize safety concerns, and describe the methods to monitor research subjects and their data to
ensure their safety, including who will monitor the data, and the frequency of such monitoring. If a
data monitoring committee will be used, describe its operation, including stopping rules and frequency
of review, and if it is independent of the sponsor (per 45 CFR 46.111(a) (6)).

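### Aim 2's glucose-only mean covers the 0-60 minutes in which the clamp is still being stabilised, so the Ex-9 effect and its Dex interaction can reflect the C-peptide rise; the scale is also unstated

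*Combined protocol and SAP*

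**What the plan says.** The analysis text appears in the Research Abstract and again in Data Analysis & Statistical Considerations, AIM-2. C-peptide during the clamp is the primary variable. "Mean values will be compared between the period of glucose only stimulation and glucose with Ex-9", by two-way repeated-measures ANOVA "using time (0-60 vs 60-120 min) and treatment (Dex vs no Dex) as the two factors". The decision rule is: "If there is an interaction with treatment we would conclude that experimental insulin resistance influences the fasting GLP-1 effect". No transformation, ratio or percentage is mentioned.

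Under Design & Procedures, AIM-2, Visits 2 and 3, dextrose begins after the 0-minute fasting sample, with a target of basal +3 mM. "This hyperglycemic clamp will be stabilized over 60 minutes", and Ex-9 then runs from 60 to 120 minutes. The same section introduces the fasting GLP-1 effect only in general terms: "this will allow a comparison of glucose-stimulated insulin secretion with and without GLP-1 action".

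Aim 3 uses the same named effect but defines it as a steady-state difference, expressed as a percentage of secretion without Ex-9.

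The hypotheses differ in wording. For Aim 2: "We hypothesize that fasting GLP-1 action will increase to compensate for experimental insulin resistance". For Aim 3: "We hypothesize that the relative effect of GLP-1r blockade on insulin secretion will be greater with progression from normal to T2DM".

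On controls: "Therefore we will enroll 6-10 subjects as controls for effects of time and repeat testing". They have the same clamps without Dex and the same analysis, and the plan expects them to show no interaction.

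**The concern.** The first averaging window is the stabilisation period itself. Followed as written, the glucose-only mean includes samples from before C-peptide has reached its plateau. It therefore understates glucose-only secretion, and the fall attributed to Ex-9 is shrunk or even reversed.

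The bias depends on how fast C-peptide rises and from what starting level. Dex could change either. The interaction, which carries the whole Aim 2 conclusion, would then partly compare rises between visits.

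Separately, the conclusion does not say whether it concerns the absolute GLP-1-dependent amount or the relative effect. A raw interaction alone cannot tell these apart if Dex raises C-peptide overall.

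**Working it through.** **Inputs.** From the documents: windows 0-60 and 60-120 min, stabilisation over 60 min, 10-15 Dex subjects, 6-10 controls, and a 30% between-subject CV (reported for insulin). Assumed, because the documents do not give them: a 20% Ex-9 reduction that is complete from minute 60, a C-peptide plateau that would otherwise stay flat, the starting level and rise time, a Dex multiplier of 1.5 (CV 15%), and a within-subject CV of 10% per period mean. The plan gives no sample-size or power figure for this interaction, so there is none to reproduce. Its figure of 8 subjects is for steps of a GLP-1 ramp.

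**Step 1: bias from the window.** If C-peptide starts at a share b of plateau and rises linearly over T minutes, the 0-60 mean as a share of plateau is R = 1 - (1 - b)T/120. A true 20% reduction then reads as 1 - 0.8/R. For b = 0.40:

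| T (min) | R | Apparent reduction |
|---|---|---|
| 15 | 0.925 | 14% |
| 30 | 0.85 | 6% |
| 45 | 0.775 | -3% |
| 60 | 0.70 | -14% |

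For b = 0.30 the range is 12% to -23%, and for b = 0.50 it is 15% to -7%. An exponential rise (b from 0.3 to 0.6, time constants 10-30 min) gives 14.3% to -14.7%.

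**Step 2: the interaction when the relative effect is unchanged.** Set the plateau at 100 without Dex and 150 with Dex. Ex-9 values are 80 and 120, a 20% reduction at both visits. The raw interaction is the Dex difference minus the no-Dex difference. In a 2x2 within-subject design the ANOVA interaction test equals a one-sample t test on this double difference. The last two columns give simulated two-sided 5% rejection rates for n = 10 to n = 15, with the Ex-9 fraction constant.

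| Share of plateau, no Dex / Dex | Difference, no Dex | Difference, Dex | Raw interaction | Apparent %, no Dex / Dex | Raw test rejects | Percentage test rejects |
|---|---|---|---|---|---|---|
| 1.00 / 1.00 | 20 | 30 | +10 | 20 / 20 | 20%-31% | about 5% |
| 0.90 / 0.90 | 10 | 15 | +5 | 11.1 / 11.1 | 9%-12% | about 5% |
| 0.80 / 0.80 | 0 | 0 | 0 | 0 / 0 | about 5% | about 5% |
| 0.90 / 0.80 | 10 | 0 | -10 | 11.1 / 0 | 26%-38% | 38%-56% |
| 0.90 / 0.85 | 10 | 7.5 | -2.5 | 11.1 / 5.9 | 6%-7% | 13%-18% |
| 0.90 / 0.867 | 10 | 10 | 0 | 11.1 / 7.7 | about 5% | 8%-10% |

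The first row is steady state, so it isolates scale. Rows two and three keep the same share at both visits. The last three let the rise differ, and there the percentage scale does not remove the problem. In the 0.90/0.867 row a true increase in absolute effect, from 20 to 30, disappears from the raw interaction.

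If the Ex-9 fraction varies between subjects and between visits (SD 10 points each), the first row's raw rate falls to 14%-21%, and the 0.90/0.80 rates fall to 16%-23% raw and 24%-35% percentage.

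**Step 3: the mirror case.** At steady state, if Ex-9 removes the same absolute amount at both visits and Dex is 1.5-fold, the raw test stays at about 5% and the log or percentage test rejects in 19%-28%. Neither scale is neutral.

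**Step 4: controls.** Without Dex, C-peptide level and rise have no Dex-related reason to differ between visits. The simulated raw rejection rate is about 4.5% (n = 6 and 10). A clean result in controls therefore says nothing about a Dex-induced change in level or rise.

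**The case against.** The fasting GLP-1 effect is one named term used in both aims, and Aim 3's procedure is described as similar to Aim 2's. A steady-state, percentage definition may therefore be intended throughout. That is plausible, but the definition appears only under Aim 3, while the Aim 2 analysis text names 0-60 minutes explicitly. The text should say what is meant.

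Several stronger readings are tempting, and the documents do not support them:

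- *A different rise at the two visits must create an interaction.* It need not: shares of 0.90 and 0.867 at 1.5-fold give a raw interaction of exactly zero.
- *The raw scale is wrong for Aim 2.* Its hypothesis is that GLP-1 action increases to compensate; only Aim 3 says relative. An absolute difference is defensible, and on that reading a raw rejection at steady state is a real finding.
- *The plan as written has a 20%-31% false-positive rate.* That figure assumes steady-state means, which the plan does not use. With 0-60 means at a common share of 0.8-0.9, raw rejection is about 5%-12%, because the two problems partly offset each other.

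It is also fair that no size here comes from trial data. The 0.90/0.80 split is an assumption, and a split of 0.90/0.85 has a much smaller effect.

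**Conclusion.** The window problem stands. It follows from two explicit statements in the plan, and it biases the primary Aim 2 contrast towards no effect or a reversed one whenever C-peptide takes an appreciable part of the first hour to rise. In the illustration starting at 40% of plateau, a true 20% reduction reads as 14% to -14%. The consequence for the interaction is conditional: a rise that differs between visits can create or hide one on either scale, and controls without Dex cannot reveal it.

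The scale point is secondary. It is an undeclared choice, not a wrong one, but it leaves the stated conclusion ambiguous.

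The direction of the window bias follows from averaging over a rise. Its size, and all rejection rates, rest on assumed Dex multiplier, rise, Ex-9 effect and within-subject CV. This should be fixed before analysis; confidence in the practical size is medium.

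**What to change.** In the Aim 2 analysis text, define each period mean from a prespecified late, steady-state part of the period, the same at both visits and consistent with Aim 3. The last 20-30 minutes is an example. The investigators should set it after checking that C-peptide has reached plateau, because a late window does not rescue a rise lasting nearly the full hour. With a linear 60-minute rise from 40%, the last 30 minutes average 85% of plateau and the last 20 minutes 90%, so a true 20% effect reads as 1 - 0.8/0.85 = 6% or 1 - 0.8/0.90 = 11%.

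State in advance whether the Aim 2 conclusion concerns the absolute or the percentage effect. Report the interaction on both scales, and claim a change in the relative effect only if the percentage or log contrast shows it. Otherwise describe the result as a change in the absolute GLP-1-dependent amount.

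The cost is two or three sentences, with no new sampling, since draws every 5-10 minutes are already planned. Each mean would use fewer samples: 3-5 in the last 20 minutes against 7-13 over 0-60. If that raised the within-subject CV from 10% to 12% (assumed), power of the percentage test for a true change from 20% to 35% would fall from 55%-75% to 47%-67% (n = 10-15, 1.5-fold, Ex-9 fraction varying).

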Visit 1: Visit 1 is a baseline study visit during which the following will take place:

- Potential subjects will review and sign the consent form with study staff.
- The participant's current medications will be recorded for review by study staff.
- A screening blood draw will be obtained to measure fasting glucose, HbA1c, hematocrit, and eGFR.

If a woman is of childbearing potential, a blood (using one teaspoon of blood drawn by a needle-stick) pregnancy test will be conducted and it must be negative prior to continuation in this study.

Visit 2: Similar to Aim 2, each participant will have a 4-hour hyperglycemic clamp procedure with the addition of the GLP-1 receptor antagonist Exendin-9 (Ex-9) to determine the *fasting GLP-1 effect*. The participants will receive an infusion of Ex-9 beginning at the 60-minute mark of the clamp procedure. Throughout the glucose infusion during visit-2, 1 ml blood samples will be taken every 5-10 minutes beginning at the -15 minute time-point and continue until the end of the 120 minute procedure. These samples will be tested immediately with a YSI glucose analyzer and the values used to adjust the glucose infusion rate to maintain stable blood glucose concentrations (a glucose clamp) throughout the experiment.

Subjects will report to the Duke Center for Living after a 12-hour fast. Study staff will obtain the participant's current body weight. At Visit-2 a skin test to confirm they do not have any sensitivity to the Ex-9 investigational compound that will be used during the infusion will be administered. The skin test is specified by the FDA as a precaution for immediate hypersensitivity; 5 ng of Ex-9 is injected intradermally and subjects are monitored for 30 minutes for a wheal/flare reaction. This skin test must be negative in order to continue with the study testing.

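### Ex-9 is always given in the second clamp hour, so the Aim-2 time term mixes clamp duration with Ex-9, and the Aim-3 cohort comparison assumes similar drift across cohorts

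*Combined protocol and SAP*

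**What the plan says.** **Aim 2, Design & Procedures.** "During both visits, the participants will receive an infusion of Ex-9 beginning at the 60-minute mark of the clamp procedure". The infusion runs "between the 60 and 120 minute time-points of the clamp procedure", and Visit 3 "will be a repeat infusion procedure identical to" Visit 2. The 6-10 control subjects have the same clamps about a week apart without dexamethasone; they are enrolled to control for time and repeat testing. The first 60 minutes serve both to stabilise the clamp and to supply the reference without Ex-9.

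**Aim 2, Data Analysis & Statistical Considerations.** C-peptide is analysed by two-way repeated-measures ANOVA in the Dex arm, with time (0-60 versus 60-120 min) and treatment (Dex or not) as factors. Controls are analysed separately in the same way. The section states: "Based on our previous studies we expect a significant time effect due to Ex-9". An interaction would be read as insulin resistance influencing the fasting GLP-1 effect.

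**Aim 3.** There is one clamp per subject: "The participants will receive an infusion of Ex-9 beginning at the 60-minute mark of the clamp procedure". The primary variable is the "difference in steady state glucose-stimulated insulin secretion with and without Ex-9", as a percentage of the level without Ex-9, compared among lean, obese and diabetes cohorts. The hypothesis in Purpose of the Study is that "the relative effect of GLP-1r blockade on insulin secretion will be greater with progression from normal to T2DM".

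**The concern.** A change in C-peptide from the first to the second hour can come from Ex-9, from the longer hyperglycaemic stimulus, or from both. Separating them needs some second-hour data without Ex-9, and the plan collects none. The Aim-2 controls omit dexamethasone, not Ex-9, so they inform on repeat visits and not on drift within a clamp.

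Two conclusions are at stake. In Aim 2, a significant time term could be read as proof of an Ex-9 effect. In Aim 3, if C-peptide rises less over the second hour in diabetic than in non-diabetic subjects, the computed reduction is larger in diabetes even when Ex-9 acts equally. The opposite pattern would conceal a real gradient.

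**Working it through.** **Step 1. Which clamps contain which periods.**

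| Group | Clamps | 0-60 min | 60-120 min |
|---|---|---|---|
| Aim 2, Dex arm (10-15) | 2 | glucose | glucose + Ex-9 |
| Aim 2, controls (6-10) | 2 | glucose | glucose + Ex-9 |
| Aim 3, all cohorts (15-20) | 1 | glucose | glucose + Ex-9 |

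The two time levels in the ANOVA coincide exactly with Ex-9 absent and present. Purpose of the Study describes Aim 3 as a graded glucose infusion while Design & Procedures describes a hyperglycaemic clamp. Those passages must be reconciled, but neither describes a session without Ex-9. The plan gives no drift figure to reproduce; its sample-size statement does not bear on this point.

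**Step 2. Aim 2, additive scale.** At visit v, let d_v be the second-hour change that would occur without Ex-9, and x_v the change due to Ex-9.

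- Time contrast at one visit: d_v + x_v. Only the sum is estimable.
- Interaction in the Dex arm: (x_3 − x_2) + (d_3 − d_2). If d_3 = d_2, drift cancels.
- Dex arm minus controls: visit-to-visit changes common to both arms also cancel. What remains is the Dex-induced change in x plus any Dex-induced change in d. The controls take no Dex, so they cannot estimate the latter.

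**Step 3. Aim 3, percentage scale.** With true fractional reduction e and drift d, the computed reduction is 1 − (1 + d)(1 − e). For two cohorts with the same e, the spurious gap is (1 − e) × (d_nondiabetic − d_T2DM). Equal drift therefore gives no gap. If e differs and d is common, the true gap is only multiplied by (1 + d).

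Take e = 25% in both cohorts (assumed), with assumed drift per hour:

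| Drift, non-diabetic / T2DM | Computed reduction | Gap |
|---|---|---|
| 10% / 0% | 1 − 1.10 × 0.75 = 17.5%; 1 − 1.00 × 0.75 = 25% | 7.5 points |
| 20% / 5% | 1 − 1.20 × 0.75 = 10%; 1 − 1.05 × 0.75 = 21.25% | 11.25 points |
| 30% / 10% | 1 − 1.30 × 0.75 = 2.5%; 1 − 1.10 × 0.75 = 17.5% | 15 points |

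Exchanging the drifts between the cohorts reverses each sign, so a true gradient would be reduced by the same amount.

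**Step 4. How often the gap alone is significant in the hypothesised direction.** Assume 12 non-diabetic versus 6 diabetic subjects, within the planned 15-20, and a two-sample t-test at two-sided 0.05. The standard error is SD × √(1/12 + 1/6) = 0.5 × SD, with 16 degrees of freedom and critical value 2.12. The noncentrality is gap / (0.5 × SD). The nominal rate in one direction is 2.5%.

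| Assumed SD (points) | Gap 7.5 | Gap 11.25 | Gap 15 |
|---|---|---|---|
| 10 | 29% | 56% | 80% |
| 15 | 15% | 29% | 47% |
| 20 | 10% | 18% | 29% |
| 30 | 7% | 10% | 15% |

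**Step 5. Can the drift be corrected from existing samples?** One could fit each subject's 30-60 min slope (4-7 samples) and project it to the middle of 90-120 min, which lies 60 minutes beyond the centre of the fit. With independent sample error s:

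- 7 samples: projected SE = s√(1/7 + 60²/700) = 2.30s, against 0.38s for the flat mean (ratio 6.1).
- 4 samples: s√(1/4 + 60²/500) = 2.73s, against 0.50s (ratio 5.5).

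If C-peptide instead approaches a plateau as 1 − exp(−t/τ), with τ of 15-30 min (assumed), the line overshoots the true level without Ex-9 by about 17-27%. A true 25% reduction is then computed as about 36-41%. Projection is too noisy and too biased to correct the estimate or to decide a conclusion.

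**The case against.** The strongest reply has four parts.

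- **The time sentence is an expectation, and the stated Aim-2 conclusion is the interaction.** This stands. A reader might infer that the plan commits to reporting the time term as its main finding, or that Aim 2 as a whole fails. The documents support neither: the hypothesis concerns a change with insulin resistance, and equal drift cancels from that test.
- **Aim 3 is defined on steady-state secretion after a stabilisation hour.** This stands in part, since a true steady state would leave little drift. But no window or criterion is given, and the reference hour is itself the stabilisation hour. Holding glucose constant does not establish that C-peptide is flat.
- **The sponsor's earlier studies may justify the attribution.** They may, but the documents show no data from them and do not say whether they included an Ex-9-free second hour.
- **The false-positive figures are built from assumptions.** This stands. Drift, SD, the Ex-9 effect, the 12/6 split (which pools lean and obese) and the test are all assumed. A reader might infer that Aim 3 has a known error rate or is biased towards its hypothesis. Nothing in the documents gives the size or direction of any drift difference between cohorts.

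**Conclusion.** The concern holds in a limited form. By design, the Aim-2 time term is the combined effect of clamp duration and Ex-9, and this needs no assumed figure. The Aim-2 interaction survives drift that is equal at both visits on the additive scale; it remains open to drift altered by dexamethasone, which the existing controls cannot measure. Aim 3 is exposed only to drift that differs between cohorts, in either direction.

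The size is unknown. Over the assumed gaps of 7.5-15 points and SDs of 10-30 points, the chance of a false finding in the hypothesised direction runs from 7% to 80%, against 2.5%. That shows the issue could matter at this sample size, not that it does. The point is worth acting on because the remedy lies mainly in what the trial may conclude.

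**What to change.** 1. In Data Analysis & Statistical Considerations, replace the sentence on the time effect with: *The time term estimates the combined effect of clamp duration and Ex-9 and will not be tested or reported as the Ex-9 effect on its own.*
2. Base the Aim-2 conclusion on one between-arm contrast instead of separate within-arm analyses. For each subject and visit, compute mean C-peptide at 60-120 min minus the pre-Ex-9 mean; take the visit-to-visit change; compare Dex subjects with the 6-10 controls already planned. State that Dex-altered drift remains an untested assumption.
3. In Aim 3, state that cohort differences reflect the Ex-9 effect only if drift within the clamp is similar across cohorts. Report each cohort's late pre-Ex-9 C-peptide slope, from samples already drawn every 5-10 minutes, as a descriptive check. Do not project that slope forward to adjust the estimate or to decide the conclusion.

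The cost is a weaker claim for the main Ex-9 effect, and a wider interval for the between-arm contrast than for the within-arm one. No extra visit, subject or blood is required.
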